9.4 Imaging Progression

Progression based on CT scans, MRI or bone scan will be defined based on location/type of lesion present as defined below.

- Soft-tissue lesions – Progression will be determined by RECIST criteria (appendix III).
- Bone lesions – the appearance of ≥ 2 new lesions, with the additional requirement that progression at first assessment be confirmed by a second scan 6 or more weeks later. The confirmatory scan must document a minimum of 2 or more additional new lesions. The date of progression is the date of the first scan that shows the change.

10 Study Data Collection and Monitoring

10.1 Data Management

This study will report clinical data using The Online Enterprise Research Management Environment (OnCore™), a web based Oracle® database utilizing study specific electronic case report forms. Key study personnel are trained on the use of OnCore and will comply with protocol specific instructions embedded within the OnCore. Patient demographics, patient specific study treatment calendars, adverse events and other information required for IND annual reporting will be placed in OnCore.

10.2 Case Report Forms

Participant data will be collected using protocol specific electronic case report forms (e-CRFs) developed within OnCore based on its library of standardized forms. The e-CRF will be approved by the study's Principal Investigator and the Biostatistician prior to release for use. The Study Coordinator or designee will be responsible for registering the patient into OnCore at time of study entry, completing e-CRFs based on the patient specific calendar, and updating the patient record until the end of required study participation.

10.3 Data and Safety Monitoring Plan (DSMP)

The study's Data and Safety Monitoring Plan will be in compliance with the University of Minnesota Masonic Cancer Center's Data & Safety Monitoring Plan (DSMP), which can be accessed at http://www.cancer.umn.edu/prod/groups/ahc/@pub/@ahc/@mcc/documents/content/ahc_content_487799.pdf

Monitoring For the purposes of data and safety monitoring, this study is classified as high risk (under a locally held IND). Therefore the following requirements will be fulfilled:

- The PI ([name]) will complete and submit a quarterly Trial Progress Report to the Masonic Cancer Center Data and Safety Monitoring Council (DSMC) with the understanding the Cancer Protocol Review Committee (CPRC) may require more frequent reporting.
- The PI will comply with at least twice yearly monitoring of the project by the Masonic Cancer Center monitoring services or designee.
- The PI will oversee the submission of all reportable adverse events per the definition of reportable in section 8.4.
- The PI will transfer affiliate site monitoring to NewLink and/or their designee who will, at a minimum, adhere to the University of Minnesota Masonic Cancer Center's DSMP.

In addition, at the time of the continuing review with the University of Minnesota IRB, a copy of the report with any attachments will be submitted to the Cancer Protocol Review Committee (CPRC).

IND Annual Reports

In accordance with regulation 21 CFR § 312.33, the IND sponsor ([name]) will submit a progress report annually. The report will be submitted within 60 days of the anniversary date that the IND went into effect. Affiliate sites will be notified approximately 60 days prior to the anniversary date of the data cut-off date and the data run date to ensure OnCore is current and eCRF's are complete.

10.4 Monitoring

The sponsor-investigator will permit study-related monitoring, audits, and inspections by the IRB, government regulatory bodies, and University of Minnesota compliance groups in addition to the monitoring requirements of the Cancer Center's Data and Safety Monitoring Plan (section 10.3).

The investigator will make available all study related documents (e.g. source documents, regulatory documents, data collection instruments, study data, etc.). The investigator will ensure the capability for inspections of applicable study-related facilities (e.g. pharmacy, diagnostic laboratory,

etc.) will be available for trial related monitoring, audits, or regulatory inspections.

10.5 Record Retention

Essential clinical documents will be maintained to demonstrate the validity of the study and the integrity of the data collected. Master files should be established at the beginning of the study, maintained for the duration of the study and retained according to the appropriate regulations.

The investigator will retain study records including source data, copies of case report forms, consent forms, HIPAA authorizations, and all study correspondence in a secured facility for at least 6 years after the study file is closed with the IRB and FDA.

In addition, the Clinical Trials Office (CTO) will keep a master log of all patients participating in the study with sufficient information to allow retrieval of the medical records for that patient. Please contact the CTO before destroying any study related records.

11 Study Endpoints

11.1 Primary Endpoint

Augmentation of Tcell activation to PA2024 as measured by ELISPOT at 14 weeks from first leukapheresis

11.2 Secondary Endpoints

- Antibodies to PA2024 as measured by ELISA
- Progression free survival
- Objective response rate as defined by Prostate Cancer Working Group -2 (PCWG2)(6)
- Overall survival and survival at two years
- Safety and tolerability
- Health related quality of life

12 Statistical Considerations

Our primary analysis will compare Tcell activation to PA2024 as measured by ELISPOT at 14 weeks between treatment groups using the two-sample t-test for unequal variance. This analysis will be completed on log-transformed data in the event that Tcell activation is skewed. A secondary analysis will be completed adjusting for any potential confounders or baseline differences using linear regression.(11)

Secondary endpoints CD54 count, antibodies to PA2024 and Tcell proliferation will be compared between groups in an unadjusted analysis using the two-sample t-test and an adjusted analysis using linear regression. Response rate will be summarized by group using contingency tables and the odds ratio for response will be estimated using logistic regression. Time to disease progression and overall survival will be summarized by Kaplan-Meier Curves and the hazard ratio estimated using Cox regression. In addition, quality of life will be measured by the FACT-P (a validated questionnaire consisting of four subscales of well-being: Physical, Social/Family, Emotional and Functional) and compared between treatment groups using the two-sample t-test for univariate analyses and multivariate linear regression for multivariate analysis.

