- Asymptomatic or minimally symptomatic disease as demonstrated by ECOG Performance Status 0 or 1 and no need for opiate pain medications to control pain/symptoms
- Adequate organ function within 14 days of study enrollment

Study Population: Men with asymptomatic or minimally symptomatic castration resistant prostatic adenocarcinoma

Sample Size: Approximately 50 subjects will be enrolled (1:1 indoximod vs placebo) at up to 5 sites

Duration of Treatment: Sipuleucel-T will be administered as standard of care either at the study center or by the referring physician. Oral indoximod /placebo will be self-administered twice daily for 6 months starting after the last infusion of sipuleucel-T. Patients will be treated for a minimum of 12 weeks of indoximod /placebo before disease progression can be declared and indoximod /placebo will not be discontinued for increasing PSA in the absence of symptomatic clinical progression.

Schema

Enrollment Plan:

Eligible, consenting patients will be enrolled to the study prior to the first leukapheresis (week 0). Randomization to either indoximod or placebo will occur at the beginning of week 4 (the week of the 3rd leukapheresis/sipuleucel-T infusion).

Treatment Plan:

Sipuleucel-T (Provenge®) - leukapheresis at weeks 0, 2, and 4 with sipuleucel-T infused 3 days later per Standard of Care

Indoximod 2400 mg/day or Placebo – begin 1 day after last sipuleucel-T infusion, continue twice daily for 6 months (24 weeks)

Immune Monitoring/Indoximod Levels:

1. At the time of screening/consent signature (1st baseline sample)
2. Any time prior to the first sipuleucel-T infusion on week 0 (2nd baseline sample)
3. After 3rd sipuleucel-T infusion on week 4
4. 2 weeks from initiation of treatment with indoximod/placebo on week 6
5. 6 weeks from initiation of treatment with indoximod/placebo on week 10
6. 10 weeks from initiation of treatment with indoximod/placebo on week 14
7. 24 weeks from initiation of treatment with indoximod/placebo on week 28

Immune Response Biomarkers - Serum Sample:

1. Any time prior to the first sipuleucel-T infusion on week 0
2. 10 weeks from initiation of treatment with indoximod/placebo on week 14

Biopsy (optional):

1. Prior to first leukapheresis on week 0
2. 10 weeks from initiation of treatment with indoximod/placebo on week 14

1 Objectives

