6.2 During Treatment

Treatment	Week	Standard of Care			Research funded lab work to be performed by local (institutional) lab	Research Related Samples	indoximod / placebo count
Leukapheresis followed by sipuleucel-T infusion	0						
	1						
Leukapheresis followed by sipuleucel-T infusion	2						
	3						
Leukapheresis followed by sipuleucel-T infusion, start indoximod /placebo day after infusion	4	Prior to indoximod /placebo Physical exam, FACT-P				9 – 10 cc green, 1 – 10 cc red (pre indoximod/ placebo)	
indoximod /placebo twice daily continuously for 6 months	5						
	6	PE, review of side effects		CBC/diff/plt, chem ¹ , U/A ²	Thyroid function, C-reactive protein, ANA panel, Auto-immune symptom list	9 – 10 cc green, 1 – 10 cc red	Reconcile Drug
	7						
	8	PE, review of side effects, FACT-P	PSA	CBC/diff/plt, chem ¹ , U/A ²	Thyroid function, C-reactive protein, ANA panel, Auto-immune symptom list		Reconcile Drug
	9						
	10	PE, review of side effects		CBC/diff/plt, chem ¹ , U/A ²	Thyroid function, C-reactive protein, ANA panel, Auto-immune symptom list	9 – 10 cc green, 1 – 10 cc red	Reconcile Drug
	11-13						
	14	PE, review of side effects, FACT-P	PSA, CT of chest, abd, pelvis, bone scan	CBC/diff/plt, chem ¹ , CTCs ³ , U/A ²	Thyroid function, C-reactive protein, ANA panel, Auto-immune symptom list	9 – 10 cc green, 2 – 10 cc red, opt biopsy	Reconcile Drug
	15-19						
	20	PE, review of side effects, FACT-P	PSA	CBC/diff/plt, chem ¹ , U/A ²	Thyroid function, C-reactive protein, ANA panel, Auto-immune symptom list		Reconcile Drug
	21-23						
	24	PE, review of side effects		CBC/diff/plt, chem ¹ , protein, U/A ²			Reconcile Drug
	25-27						
28	PE, review of side effects, FACT-P	PSA, CT of chest, abd, pelvis, bone scan,	CBC/diff/plt, chem ¹ , U/A ²	Thyroid function, C-reactive protein, ANA panel, Auto-immune symptom list	9 – 10 cc green, 1 – 10 cc red	Final Reconcile Drug	

1- chem to include Bun/creatinine, Na, K, Ca, Mg, tot. bili, AST, ALT, alkaline phosphatase, LDH, albumin, total protein

2- Proteinuria – any protein ≥ 2+ on dipstick or new urine active sediment/EOS should be evaluated per section 5.2.2

3- CTCs - circulating tumor cells

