6.2.1 Immune Monitoring Studies

At each time point in the previous table nine 10 cc green top tubes and one 10 cc red top tube will be collected. An additional serum sample (one 10 cc red top tube) will be collected at week 14.

All blood samples will be sent to Translational Therapy Laboratory (TTL) at University of Minnesota. Refer to the affiliate lab manual for the specimen specific shipping instructions.

T, NK, Treg by immunophenotype, NK cell function [CD107a and IFN production] measurements will be done in peripheral blood and tumor tissue at the Translational Therapy Laboratory (TTL) at University of Minnesota.

ELISPOT to PA2024, ELISA to measure antibody to PA2024 will be done at above specified time points from the peripheral blood by Dendreon.

Serum kynurenine, tryptophan, K/T ratio, and indoximod levels will be measured from peripheral blood at the specified time points by Newlink.

The pre and week 14 serum sample will be analyzed for immune biomarkers by Newlink.

If the patient consents at time of enrollment, aliquots of leftover serum will be stored from each blood draw at -80 degrees C in the Masonic Cancer Center's TTL for future testing. Permission to store leftover samples will be embedded in the treatment consent.

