7.5 Breaking the Blind

The blind shall be maintained throughout the conduct of the trial unless it is felt necessary to break the blind in a specific case in the interest of patient safety. In general, the blind will be broken after all the data are recorded, locked, and analyzed. The study statistician ([name]) will provide each site's investigational pharmacy with the treatment code key. Any request to break a blind will be discussed with the sponsor/investigator ([name]) and NewLink.

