9.1 Immune Response to PA2024

The frequency of antigen specific, cytokine producing cells will be determined by an ELISPOT assay. ELISPOT assay will use whole PBMC to assess interferon gamma production in response to the immunizing protein PA2024. Increase in number of ELISPOT responses to PBMC in patients in the treatment arm will be compared to those in control arm.

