12.1 Power and Sample Size

Previous studies showed that subjects treated with Sipuleucel-T had an interferon-gamma ELISPOT response to PA2024 of ~24 spots per 3×10^5 mononuclear cells at 14 weeks with a coefficient of variation of approximately 1.6. Assuming that we observe a similar coefficient of variation and a 2.5 fold increase in the ELISPOT assay (an average of ~60 spots per 3×10^5 mononuclear cells) in those treated with Sipuleucel-T plus the addition of indoximod, a total sample size of 50 (25 subjects per group) will provide 80% power to reject the null hypothesis at the 0.05 level using a two-sample t-test to compare log-transformed expression levels between the two groups.

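### The primary week-14 ELISPOT test is valid but ignores the pre-drug week-4 ELISPOT the trial already collects, and the adjusted analysis names no covariates

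*Combined protocol and SAP*

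**What the plan says.** Section 12 states that the primary analysis "will compare Tcell activation to PA2024 as measured by ELISPOT at 14 weeks between treatment groups using the two-sample t-test for unequal variance", moving to the log scale if the data are skewed. No covariate enters. It continues: "A secondary analysis will be completed adjusting for any potential confounders or baseline differences using linear regression". No covariate is named there either.

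Section 12.1 sizes the trial on the unadjusted comparison of log values: "a total sample size of 50 (25 subjects per group) will provide 80% power to reject the null hypothesis at the 0.05 level". Its inputs are about 24 spots on control, about 60 on indoximod (2.5-fold) and a coefficient of variation of about 1.6.

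Three places establish the week-4 measurement:
- The schema lists an immune-monitoring sample "After 3rd sipuleucel-T infusion on week 4".
- The week-4 row of the table in section 6.2 reads "9 – 10 cc green, 1 – 10 cc red (pre indoximod/ placebo", so the draw is labelled as preceding study drug. The schema and section 5.2 start study drug the day after that infusion.
- Section 6.2.1 says "ELISPOT to PA2024, ELISA to measure antibody to PA2024 will be done at above specified time points".

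Section 9.1 describes the comparison differently: "Increase in number of ELISPOT responses to PBMC in patients in the treatment arm will be compared to those in control arm". It does not say what the increase is measured from.

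**The concern.** The objective is augmentation of the response to sipuleucel-T. The week-4 ELISPOT is each man's response to the full vaccine course before any study drug, so it bears directly on that question. Leaving it out of the primary model means chance differences between arms in vaccine response stay in the error term. With 25 per arm such differences are not small, and ELISPOT is highly variable.

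The secondary regression does not settle the matter. If covariates are chosen from the differences observed, several adjusted results can be produced and nothing fixes which one is reported. Nothing commits that analysis to using week 4.

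Section 9.1 adds uncertainty. Its wording could mean a within-patient change or simply a higher level in one arm, and only the second agrees with section 12.

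**Working it through.** **Inputs from section 12.1.** CV 1.6, 2.5-fold effect, 25 per arm, alpha 0.05 (taken as two-sided, since that reproduces the stated power).

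**Input not in the documents.** The week-4 to week-14 correlation ρ on the log scale, shown as a range.

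**Step 1: reproduce the plan's power.**
- Log-scale SD = √ln(1 + 1.6²) = 1.127.
- Effect = ln 2.5 = 0.916.
- Standardised effect = 0.916 / 1.127 = 0.813.
- Noncentral t, 48 df: power 0.804, matching the stated 80%.

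**Step 2: precision of the unadjusted test.**
- SE of the log difference = 1.127 × √(2/25) = 0.319.
- 95% interval factor = exp(2.01 × 0.319) = 1.90 either way.
- If week 4 has the same CV (assumed), one SE of chance imbalance at week 4 is exp(0.319) = 1.38-fold. The t-test's standard error already allows for such imbalance, so it costs precision and causes no bias.

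**Step 3: add log week-4 ELISPOT.** Residual SD = 1.127 × √(1 − ρ²), with 47 df. The simulated column uses HC2 robust standard errors and a random covariate (40,000 trials per setting).

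| ρ (assumed) | Variance removed | Formula power | Simulated power | 95% interval factor |
|---|---|---|---|---|
| 0 | 0% | 0.804 | 0.799 | 1.90 |
| 0.3 | 9% | 0.839 | 0.832 | 1.84 |
| 0.5 | 25% | 0.902 | 0.897 | 1.74 |
| 0.7 | 49% | 0.976 | 0.972 | 1.58 |

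Simulated type I error was 0.049 to 0.052.

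**Step 4: robustness.**
- *Dropout.* Fifty is both the enrolment target and the powered number, with no allowance stated. At 22 per arm, unadjusted power is 0.750; adjusted it is 0.788, 0.860 and 0.958 at ρ = 0.3, 0.5 and 0.7.
- *Unequal variance.* Under the null with 28 v 22 patients, treated residual SD 1.5 times control and ρ = 0.5, type I error is 0.064 with ordinary standard errors, 0.054 with HC2 and 0.051 for the planned t-test. Robust standard errors are therefore needed.
- *Missing week-4 values.* With 20% missing at random and filled in blind to arm, power is about 0.82, 0.87 and 0.94 at ρ = 0.3, 0.5 and 0.7.
- *Zero counts.* Lognormal means with mean 24 and CV 1.6, plus Poisson counting, give about 2% zeros. Using log(count + 1), the t-test has power 0.78 and the adjusted model 0.80, 0.86 and 0.94.
- *Change from week 4*, one reading of section 9.1. Its SD is 1.127 × √(2(1 − ρ)), and power is 0.663, 0.804 and 0.953 at ρ = 0.3, 0.5 and 0.7. This is never better than covariate adjustment and is worse than no adjustment at low ρ.

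**The case against.** The planned test is a complete, correctly powered analysis of a randomised comparison and needs no covariate choice. Preferring adjustment is a question of efficiency, and the gain rests on a correlation the documents do not report. Week 4 is ten weeks before the endpoint and close to the last infusion, so it may predict week 14 poorly. At ρ = 0.1 and 0.2 formula power is only 0.808 and 0.820. All of this stands: the higher figures are scenarios, not demonstrated losses.

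Two further objections carry less weight. First, the week-4 draw may follow randomisation, which section 4.3 places at the beginning of that week, and the ±3-day window in section 6 could let a late draw fall after the first dose. But section 6.2 explicitly labels the sample as pre-drug, and a blinded assignment cannot influence a pre-dose value. A rule for mistimed samples closes the gap. Second, the secondary regression could already include ELISPOT from week 4 or from the two pre-vaccine samples. It could, but nothing commits it to do so, and the primary test would still not benefit.

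It is also fair to say that section 9.1 is ambiguous and not in plain conflict with section 12, and that HC2 is marginally less protective than the t-test in the stress case (0.054 v 0.051).

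**Conclusion.** The concern holds, as a recommended improvement and not as a correction of an error. The primary test is valid and its 80% power is right, but a pre-treatment measure of the same quantity, already scheduled and assayed, is left out of it, and the adjusted analysis is not fixed in advance.

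The power gain at 25 per arm is about 3 points at ρ = 0.3, 10 at 0.5 and 17 at 0.7. The downside near ρ = 0 is about half a point. These figures assume log-normal ELISPOT values with the CV of section 12.1 and a correlation that must be taken as unknown. The case for naming the covariates in advance does not depend on the correlation.

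**What to change.** Before unblinding, amend section 12 as follows:
- Make the primary analysis a linear model of log week-14 ELISPOT on arm and log week-4 pre-drug ELISPOT, with HC2 standard errors. Report the adjusted geometric-mean ratio with its 95% interval.
- Fix the log scale and the offset for zero counts.
- Impute a missing week-4 value blind to arm, for example with the overall mean, with or without a missing indicator. Treat a week-4 sample drawn after the first dose as missing. Do not substitute pre-vaccine values.
- Keep the unadjusted unequal-variance t-test as a sensitivity analysis.
- Name the covariates of any further regression. Include site only if the site randomisation packets are blocked within site, with a pooling rule for small sites; otherwise make it a sensitivity analysis.
- Reword section 9.1 to describe the same comparison.

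The cost is one degree of freedom and a few sentences of text. No new samples, assays or patients are needed, and the sample size stays at 50. Timing should be feasible: section 7.5 says that in general "the blind will be broken after all the data are recorded, locked, and analyzed". Because the study statistician supplies the treatment code to the pharmacies, the amendment is most credible if dated before any week-14 results are linked to that code.

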4.3 Patient Randomization

Each site will do their own randomization through the institutional investigational pharmacist using a randomized packet provided by the study statistician at the time of study site activation.

To be eligible for randomization a patient must have received all 3 doses of sipuleucel-T.

Patients will be randomized 1:1 to either indoximod or an identical looking placebo by notifying the institutional investigational pharmacist at the beginning of week 4 (the week of the 3rd leukapheresis/sipuleucel-T infusion).

Patients who are not randomized (ineligible or refuses) will be deemed unevaluable, removed from study and followed per standard of care, independent of this study.

Patients/research staff will not be un-blinded for the duration of the study except in the event of a medical emergency per section 7.5.

5 Treatment Plan

In order to provide optimal patient care and to account for individual medical conditions, the treating physician's discretion may be used in the prescribing of all supportive care drug therapy.

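### Does the log-scale primary test need a written rule for zero ELISPOT counts?

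*Combined protocol and SAP*

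**What the plan says.** Section 12 makes the primary analysis a two-sample t-test for unequal variance on T-cell activation to PA2024 at 14 weeks, with this condition: "This analysis will be completed on log-transformed data in the event that Tcell activation is skewed". Section 12.1 powers the log-scale version only, "using a two-sample t-test to compare log-transformed expression levels between the two groups". Its inputs are a control response of about "24 spots per 3×10^5 mononuclear cells at 14 weeks", "with a coefficient of variation of approximately 1.6", and a 2.5-fold increase to about 60 spots. It concludes that "a total sample size of 50 (25 subjects per group) will provide 80% power" to "reject the null hypothesis at the 0.05 level".

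Sections 6.2.1, 9.1, 11.1, 12 and 12.1 give no added constant, detection limit, substitution value, background-subtraction rule or exclusion rule, and no expected share of zeros.

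On who could see treatment codes, Section 4.3 has each site randomize "using a randomized packet provided by the study statistician at the time of study site activation", and in Section 7.5 the study statistician gives each site's "investigational pharmacy with the treatment code key". Section 7.5 also says that the blind is in general lifted only after the data are recorded, locked and analyzed. Section 4.3 bars unblinding of research staff except in a medical emergency.

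**The concern.** The endpoint is a count, the only powered test takes its logarithm, and a patient with no spots has no logarithm. The log branch is the one that will be used: a log-normal variable with a coefficient of variation of 1.6 has skewness 3 × 1.6 + 1.6³ = 8.9, so any ordinary criterion would call it skewed.

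Two analysts could then follow Section 12 on the same data and differ. One adds a constant. The other lets software set log(0) to missing, which removes randomized patients because of their outcome. If indoximod worked only by turning non-responders into responders, dropping them would hide the effect. The statistician also supplies the randomization packets and the code key, and no separate blinded analyst is named, so a choice made with knowledge of the arms is not formally excluded. At stake are a primary verdict that depends on an unwritten step, and some inflation of type I error.

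**Working it through.** **The plan's power.** Log-scale SD = sqrt(ln(1 + 1.6²)) = sqrt(ln 3.56) = 1.127. Effect = ln 2.5 = 0.916. Standard error with 25 per arm = 1.127 × sqrt(2/25) = 0.319. Normal approximation: 0.916/0.319 − 1.96 = 0.915, giving power 0.82. The noncentral t with 48 df gives 0.804. Section 12.1 does not state sidedness; two-sided 0.05 is assumed and reproduces the stated 80%. This model contains no zeros.

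**How likely is a zero?** The documents give no rate, so two count models bracket it.

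- Rounded log-normal: the log mean is ln 24 − 1.127²/2 = 2.54 in control and ln 60 − 1.127²/2 = 3.46 on indoximod. The chance of falling below 0.5 is 0.0020 and 0.0001. At least one zero among 50: 1 − exp(−25 × 0.0021) = about 5%.
- Poisson counts around the log-normal: zero probability 2.1% and 0.4%. At least one zero: 1 − 0.979²⁵ × 0.996²⁵ = about 47%, and 46% by simulation. If the count pooled three times as many cells (an assumption), this falls to 6%.

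**How often do rules disagree at p<0.05?** Simulated trials, 25 per arm, Poisson-log-normal counts, means 24 and 60, with extra zeros added at an assumed rate in both arms:

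| | 0% | 2% | 5% | 10% |
|---|---|---|---|---|
| Trials with any zero | 46% | 81% | 96% | >99% |
| +0.5 v +1 | 0.9% | 2.8% | 4.1% | 5.0% |
| +1 v +5 | 3.0% | 5.3% | 7.9% | 10.1% |
| +0.5, +1, +5 not all alike | 4% | 8% | 12% | 16% |
| Drop v +1 | 5.8% | 13% | 21% | 30% |
| Drop v +1, no true effect | 3.1% | 4.0% | 5.1% | 6.3% |

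With no true effect, +0.5 v +1 disagree in 0.4 to 0.6% of trials and +1 v +5 in 1.4 to 1.8%.

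With rounded log-normal counts, drop v +1 disagreement at the design effect is about 1.5%. With negative binomial counts (zeros in 19% of control and 14% of indoximod patients), four rules that keep everyone (+1, +0.5, zero set to 0.5, zero set to half the smallest positive value) fail to agree in 3.3%.

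**Type I error.** Each log rule used alone rejects in 0.047 to 0.051 of null trials. Taking the best of +0.5, +1 and +5 after seeing all three gives 0.055 to 0.060. Values of 0.066 to 0.089 arise only if dropping zeros is among the options.

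**Would a fixed rule gain power?** Power at 0/2/5/10% added zeros in both arms: +0.5 gives 0.78/0.69/0.58/0.45; +1 gives 0.78/0.71/0.62/0.50; +5 gives 0.78/0.74/0.68/0.59; a rank test 0.76/0.72/0.67/0.55; dropping 0.76/0.74/0.73/0.71. With 10% zeros in control and none on indoximod the order turns: +1 gives 0.90, dropping 0.73. No rule is best throughout, and the documents do not say which case applies.

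**The case for a change.** The best case for a change is that it costs one sentence and would make the primary verdict reproducible. Dropping zeros is not far-fetched, since software may do it silently, and nothing in the plan forbids it. In the extreme case of an effect acting only on zeros (20% v 0%, assumed), dropping has power 0.05 against 0.29 for log(spots + 1). Even among rules that keep everyone, three constants are not unanimous in up to 16% of trials at 10% added zeros, and their power differs materially. The statistician's access to the code is also a fair point.

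Much of this stands as description. It falls short as a reason to amend. Section 12 compares the randomized groups, and discarding a patient with a measured result of zero answers a different question; a competent analyst would see the missing values and not accept them. The larger percentages and the power losses come from added zeros, which are assumed. The power lost with many zeros is a property of such data: writing down a constant does not restore it. A sentence that requires some constant, without grounds in the documents for choosing one, leaves the differences between constants where they were. Section 7.5's general rule that analysis precedes unblinding limits selection by result, though it does not exclude it.

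**Conclusion.** This is a detail the plan leaves out and analysts fill sensibly. No stated rule is wrong, the 80% power reproduces, and every log rule examined keeps its level. If the analyst adds a small constant and retains everyone, the choice between two constants changes the verdict in about 1 to 10% of trials at the full 2.5-fold effect and in about 0.4 to 1.8% under no effect. Deliberate selection among three such constants takes type I error to at most about 0.06. These sizes rest on Poisson-log-normal counts with 0 to 10% added zeros; rounded log-normal counts make zeros rare. The gap would matter more if zero-count patients were dropped or zeros proved common, and the documents indicate neither. A written rule could not be shown to be the better one and might cost power, so the plan can stand.
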